10.2 Method of Assigning Subjects to Treatment – Randomization

To generate the randomization scheme, a random number generator program known as Research Randomizer will be used (Urbaniak & Plous, 2013). Subjects will be randomly

assigned to unequal treatment groups in a 3:1 ratio. A random number scheme will be created containing 15 sets of numbers with 4 unique numbers per set (1-4) [total of 75 numbers corresponding to 75 subjects]. Of the 4 numbers per set, patients assigned to numbers 1, 2, or 3 will receive FGF-2 and patients assigned to number 4 will receive placebo. Once the random numbers are generated, the pharmacy will create an Excel spreadsheet with the FGF-2 and placebo assignments corresponding to the numbers that were generated.

Randomization assignments will be done centrally by the MEE pharmacy. Subjects are assigned to treatment by placing the subject's name on the next available line of the spreadsheet. For subjects treated at MEE, the pharmacist uses this information to prepare the proper treatment for the subject. For subjects at the Willford Hall location, the randomization assignment will be communicated to designated staff at Willford Hall via secure email.

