1. SYNOPSIS

Protocol No.: 16-043H

TITLE: Fibroblast Growth Factor Regeneration of Tympanic Membrane Perforations
INVESTIGATIONAL PRODUCT: Human fibroblast growth factor-2 (FGF-2/bFGF/FGF-II) in a gelatin sponge, adhered by fibrin glue
INDICATION: Treatment of chronic non-healing tympanic membrane perforation
PHASE OF DEVELOPMENT: Phase 2
INVESTIGATIONAL SITES/LOCATIONS: Mass Eye and Ear Infirmary, Boston, Massachusetts
STUDY DESIGN: A Phase II randomized trial will be initiated to evaluate efficacy as the primary measureable outcome. Eligible and consented patients will be randomized in a 3:1 ratio to the optimal biologic dose (OBD) of FGF-2 or placebo (sterile water) during the Randomized Treatment Phase. Application of the study treatment may occur at the initial Screening Visit (pending all eligibility requirements can be confirmed) or at Visit 1 and may be repeated at each follow up visit as needed for a maximum of three treatments in the Randomized Treatment Phase. These follow up visits will occur three weeks (+/- 7 days) from the last treatment application. During these visits, the subject's tympanic membrane will be examined, photographed, and additional otologic tests will be performed. If the perforation is found to be closed during these visits, then the subject will report in 2 months (+/- 7 days) for a final study visit. If the subject's TMP has not closed after the third and final application of their assigned treatment group, then the blind on the subject's randomization status will be broken, and placebo patients will be crossed over to receive unblinded study drug. Again, the subject may be given up to three additional treatments in the unblinded crossover phase. The follow up visits will follow the same schedule, occurring three weeks (+/- 7 days) from the last treatment. The same otologic procedures will be performed as in the previous visits. All subjects will report for a final study visit 2 months (+/- 7 days) after their last follow up visit when the perforation is determined to be closed or when the subject has completed the maximum number of study visits without perforation closure. The study will be completed for reporting purposes after all subjects have completed the 2 month (+/- 7 days) follow up final visit.
NUMBER OF SUBJECTS (PLANNED): 75

DIAGNOSIS AND MAIN CRITERIA FOR INCLUSION:

Key inclusion criteria:

- Age 18 years and older
- Dry tympanic membrane perforation of greater than 3 months duration

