- 3) Place a human fibroblast growth factor-2 (FGF-2) soaked pledget of bioabsorbable gelatin sponge larger than the tympanic membrane so the tympanic membrane is completely covered.
- 4) Secure the pledget in place with several drops of fibrin glue.
- 5) After the effects of the topical anesthetic have worn off, if any, the patient is released with the following instructions:
 - a) Avoid violently sniffling or blowing the nose
 - b) Sneeze and cough naturally through the mouth without occluding the mouth with the hand.
 - c) Use cotton balls covered with petroleum jelly on the outer surface when washing the hair and bathing. This is needed to help keep water out of the ear.
 - d) Avoid using a hearing aid in the treated ear.
 - e) Avoid flying, using elevators in tall buildings, and other situations involving substantial changes in air pressure.
 - f) Avoid swimming.

DISCONTINUATION FROM TREATMENT:

Reasons for permanent discontinuation include the following:

If the first treatment does not result in complete closure, subsequent treatments will not be administered if any ear complications occur in the treated ear, including but not limited to infection, moderate to severe pain, moderate to severe irritation, or clinically significant sensorineural hearing loss. All subjects will complete all safety follow up visits.

PRIMARY ENDPOINT:

The tympanic membrane and surrounding structures will be examined every 21-days (+7 days) for up to three visits. Adverse events will be recorded at all visits. Routine laboratory tests will be performed at the screening visit and at the final study visit. Vital signs will be assessed at each study visit and changes in clinical examination findings will be noted.

SECONDARY ENDPOINTS:

- Tympanic membrane perforation closure determined by otoscopic exam and photographic documentation
- Pure-tone and speech discrimination scores as measured by pre- and post-treatment audiograms
- Mobility of the tympanic membrane as measured by tympanometry
- Salvage rate of FGF-2 in patients who fail placebo

STATISTICAL ANALYSIS:

The target enrollment of 75 subjects will provide sufficient power while also accounting for potential retention issues. The primary endpoint is to confirm the efficacy of

FGF-2 in subject with TMR by testing the hypothesis that the rate of subject with complete closure of the TMR will be superior to that placebo.

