The sample size is calculated in 3:1 ratio to FGF-2 treatment group or placebo to provide more than 90% power to detect a clinical significant difference at a two-sided significance level of 0.05 using a Fisher's exact test. To allow for 5% dropouts, 45 patients of FGF-2 treatment group and 15 patients of placebo are required.

Data after discontinuations for any reason will not be imputed through the final schedule visit. This subject will be considered as not-improvement.

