17.1 Determination of Sample Size

The target enrollment of 60 subjects will provide sufficient power while also accounting for potential retention issues. With recruitment of only 44 subjects, we will reach a power of .80. This gives room for some attrition, although we think it will not be more than 5%.

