17.5 Efficacy Analysis

Efficacy data from the Randomized Treatment phase will be evaluated by inspection, using student T-test, Cochran Mantel Hansel, or Kruskal-Wallis tests as appropriate; without conservation of alpha at 0.05. An interim analysis will be completed after approximately 50% of the study subjects (n=30) have been accrued.

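### The planned sample size is 75 in some places and 60 in others, and the randomization list described (15 sets of 4) yields 60 assignments, not the stated 75

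*Combined protocol and SAP*

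**What the plan says.** Three places give 75:

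- Synopsis header: "NUMBER OF SUBJECTS (PLANNED): 75".
- Synopsis, statistical analysis: "The target enrollment of 75 subjects will provide sufficient power while also accounting for potential retention issues".
- Section 10.2, on the randomization list: "15 sets of numbers with 4 unique numbers per set (1-4) [total of 75 numbers corresponding to 75 subjects". Within each set, numbers 1 to 3 mean FGF-2 and number 4 means placebo.

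Three places give or imply 60:

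- Synopsis, statistical analysis, directly after the target of 75: "To allow for 5% dropouts, 45 patients of FGF-2 treatment group and 15 patients of placebo are required".
- Section 17.1: "The target enrollment of 60 subjects will provide sufficient power while also accounting for potential retention issues". It adds "With recruitment of only 44 subjects, we will reach a power of .80" and, on losses, "This gives room for some attrition, although we think it will not be more than 5" percent.
- Section 17.5: the interim analysis comes "after approximately 50% of the study subjects (n=30) have been accrued".

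The synopsis therefore contradicts itself as well as Section 17.1. No section explains how the two numbers relate.

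**The concern.** The number to be randomized and the length of the allocation list are basic design parameters, and here both can be read two ways. The sentence in Section 10.2 is also wrong within itself, since its set count and set size do not give its total.

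The consequences are practical. The pharmacy builds its spreadsheet from Section 10.2 and enters each subject on the next free line. If 75 is intended, the list as described runs out after subject 60, and the last 15 assignments would have to be produced during a double-blind trial by a step the protocol does not describe. If 60 is intended, the synopsis header, the synopsis target and the bracket in Section 10.2 state the wrong number. Either way the protocol does not say when enrolment ends. Because an interim analysis is planned, the choice between stopping at 60 and continuing to 75 could be made after interim data exist. It should be fixed beforehand.

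**Working it through.** **Inputs.** Section 10.2: 15 sets, 4 numbers per set, 3 FGF-2 to 1 placebo, stated total 75. Synopsis: planned 75; 45 + 15 required after allowing for 5% dropouts; more than 90% power, two-sided 0.05, Fisher's exact test. Section 17.1: target 60, power .80 at 44, attrition not more than 5%. Section 17.5: interim at n = 30, about 50%.

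**1. Reproduce the list total.** Sets × set size = 15 × 4 = 60, made up of 15 × 3 = 45 FGF-2 and 15 × 1 = 15 placebo. The stated 75 is not reproduced; the shortfall is 75 − 60 = 15. Fifteen sets would give 75 only with five numbers per set, but the text fixes four. Moreover 75 / 4 = 18.75, so no whole number of sets of four gives 75 (18 sets give 72, 19 give 76).

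**2. Compare with the other figures.**

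| Source | Figure | Implied total |
|---|---|---|
| Synopsis header | 75 | 75 |
| Synopsis target enrolment | 75 | 75 |
| 10.2, bracket | 75 | 75 |
| 10.2, 15 sets of 4 | 15 × 4 | 60 |
| Synopsis arm sizes | 45 + 15 | 60 |
| 17.1 target enrolment | 60 | 60 |
| 17.5 interim | 30 / 0.50 | 60 |

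Against 75, an interim at 30 is 30 / 75 = 40%; half of 75 is 37.5.

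**3. Can dropout reconcile them?** The 60 already carries the allowance: 57 / 0.95 = 60. Inflating 60 by 5% again gives 60 / 0.95 = 63.2, rounded up to 64 (or 60 × 1.05 = 63). Reaching 75 from 60 needs a loss of 1 − 60/75 = 20%, four times the stated maximum.

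**4. Can 75 be enrolled and 60 evaluable?** The synopsis and Section 17.1 use the same sentence about target enrolment with only the number changed, so both are enrolment targets. Section 10.2 also ties 75 to randomization numbers, which excludes a screened-versus-randomized reading.

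**5. Side check on power.** The plan gives no closure rates, so the check is anchored to its own figure of .80 at 44. Assumptions: the 44 are split 33:11, the test is two-sided Fisher at 0.05, placebo closure runs from 5% to 50% in steps of 5 points, and the FGF-2 rate is solved at each step to give exactly 80% at 33:11. Exact power is then:

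| Total | Split | Power |
|---|---|---|
| 60 | 45:15 | 0.905–0.929 |
| 75 | 56:19 | 0.960–0.970 |
| 75 | 57:18 | 0.952–0.967 |

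Under that anchor, the synopsis figure of more than 90% agrees with 45 + 15.

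**The case against.** The best defence accepts the arithmetic and disputes its weight. No bias is shown, the first 60 allocations are unaffected, and a longer list takes only a few more sets from the same program. The plan has no stopping boundary or alpha-spending rule tied to the information fraction, so whether 30 subjects is 40% or 50% changes no stated decision rule. All of that is correct. It limits the consequence but does not remove the conflict: two totals cannot both govern when enrolment closes.

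A second objection is that the power reassurance is conditional. This stands. It depends on the plan's .80 at 44 being right and on the assumed split and test. At assumed closure rates of 80% versus 40%, for example, exact power at 45:15 is about 0.77. At 57 subjects after a 5% loss, with dropouts excluded, the same anchor gives 0.869–0.915 for a 43:14 split and 0.903–0.917 for 42:15. The power figures should not be read as confirming that either total is adequate.

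A third objection is that the documents do not show which number is later. An increase to 75 that was never carried into Sections 17.1 and 17.5 and the set count is as plausible as a stray 75. This also stands, so the sponsor must say which number is meant.

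**Conclusion.** The concern holds and must be fixed. The list described in Section 10.2 has 60 lines, not 75, and the planned sample size is inconsistent across the synopsis and Sections 10.2, 17.1 and 17.5. The discrepancy is 15 subjects: 20% of 75, or 25% above 60. The power statement, the dropout allowance, the arm sizes, the set count and the interim number all belong to 60. Only the two synopsis statements and the bracket in Section 10.2 say 75.

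This conclusion rests on the plan's own numbers and needs no assumption. No loss of power is claimed; the power check alone depends on assumptions and does not bear on the conflict.

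**What to change.** The sponsor should confirm the intended total and state it identically everywhere.

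- **If 60:** change 75 to 60 in the synopsis header, the synopsis target enrolment and Section 10.2, so that the list reads 15 sets of 4, 60 numbers, 45 FGF-2 and 15 placebo. The interim stays at 30. Cost: wording in three places, with no new list and no extra subjects.
- **If 75:** generate 19 sets of 4 in advance (19 × 4 = 76 lines). State that the last set may be incomplete, which gives 56:19 or 57:18. Correct the 45 + 15 statement and Section 17.1, move the interim to about 38 (75 / 2 = 37.5), and restate the power for 75. Cost: four sets beyond the 15 described, wording in the synopsis and Sections 10.2, 17.1 and 17.5, and 15 more subjects than Section 17.1 plans.

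In either case it would help to add the closure rates behind the power figures, so that the chosen total can be checked. That is a separate gap and does not decide between 60 and 75.

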Once the subject completes Visit 1, Visit 2, and Visit 3, the subject will come back for Visit 4 (+/- 7 days). During this visit, the perforation will be examined again. If the perforation has not closed completely at this visit, then the blind on the subject's randomization status will be broken. If the subject was randomized to placebo, s/he will be crossed over to receive unblinded FGG-2 treatment. If the subject was randomized to FGF-2 treatment, s/he will receive no further study treatment and return in two months (+/- 7 days) for the final follow up visit.

If crossed-over to unblinded FGF-2 treatment, the subject may be given up to three additional treatments. The follow up visits will occur three weeks (+/- 7 days) and the same otologic procedures will be conducted as mentioned before (See Section 13.1, Schedule of Assessments). If the perforation is found to be closed during these visits or when the subject has completed the maximum number of study visits without perforation closure, then the subject will report in 2 months (+/- 7 days) for a final visit. The study will be completed for reporting purposes after all subjects have completed the 2 month (+/- 7 days) follow up final visit.

6. Discussion of Study Design

The investigator and the subject will be blinded to treatment assignment during the Randomized Treatment phase. Subjects whose perforations fail to close during the randomized treatment phase will crossover to the Unblinded Crossover Phase. During the crossover phase, only those subjects who failed placebo will receive unblinded FGF-2 treatment. The rationale for using a dose of 20 μ g in 0.2ml is based on the maximum effective dosages as reported in humans of TMR closure with FGF-2 (Kanemaru et al., 2011).

The subjects, physician, and other study staff members will remain blinded to the treatment arm during the randomized treatment phase as the pharmacy will oversee the randomization process. During the Randomized Treatment phase, the pharmacy will provide the appropriately blinded vial of either FGF-2 or placebo solution as needed upon the request from the physician. Only those subjects who fail the randomized treatment phase will crossover into the unblinded crossover phase. Documentation of the cross-over will be made in the Case Report Forms as well as in the randomization log managed centrally by the dispensing pharmacy.

7. Selection of Study Population

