14.4 Visit 4, 64 days after the first treatment (± 7 Days)

The following procedures will be performed:

- Study Drug administration- *If the TMP is not completely closed, then the blind on the subject's randomization status will be broken. Placebo subjects will be crossed over to FGF-2 treatment arm at this visit.*
- Vital Signs
- Review of Prior/ Concomitant medication(s)
- TM photography
- Audiogram
- Assessment of Possible Adverse events

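### Fixed, published blocks of four with one placebo each, together with code-breaking at Visit 4, can reveal block-mates' arms to anyone who can place subjects on the list

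*Combined protocol and SAP*

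**What the plan says.** Section 10.2 describes the list as "15 sets of numbers with 4 unique numbers per set (1-4) [total of 75 numbers corresponding to 75 subjects" and states that "patients assigned to numbers 1, 2, or 3 will receive FGF-2 and patients assigned to number 4 will receive placebo". Subjects are assigned by "placing the subject's name on the next available line of the spreadsheet", so blocks fill consecutively. The pharmacy at the main site holds one list for both sites, and no stratification by site is mentioned. For the second site, "the randomization assignment will be communicated to designated staff at Willford Hall via secure email".

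Section 5.1 gives the Visit 4 rule: "If the perforation has not closed completely at this visit, then the blind on the subject's randomization status will be broken". Section 14.4 adds: "Placebo subjects will be crossed over to FGF-2 treatment arm at this visit". That treatment is open, so the clinic sees which arm the subject had been in.

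Section 6 states the blinding commitment: "The subjects, physician, and other study staff members will remain blinded to the treatment arm during the randomized treatment phase".

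Three further places bear on the point. Section 16.2 puts a randomization number on the case report form. Section 4.1 bases the primary objective on photographs before and after treatment. Section 13.2 requires closure to hold at a 21-day visit and again at a later test-of-cure visit.

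**The concern.** In most trials, working out a block-mate's arm needs an emergency code break or a telltale side effect. Here a scheduled rule reveals arms one at a time while other members of the same block may still be under assessment. Because each block has exactly one placebo, one revealed placebo failure settles the other three.

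The leak runs mostly one way, since it identifies FGF-2 subjects. If the person judging closure, or deciding whether an ear is closed or needs another application, knew the arm, any resulting error would tend to favour the drug. Closure is open to judgement at the margin: the 87-subject study cited in Section 3.2 separates complete closure from pinholes (5.7%).

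**Working it through.** **1. The plan's own figure.** 15 sets × 4 = 60, not the 75 stated in Section 10.2, and 75 / 4 = 18.75 is not a whole number of blocks. The figure does not reproduce. The block structure is the same under either total.

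**2. What one code break reveals in a block of four (3 FGF-2, 1 placebo).**
- The placebo subject is revealed: P(FGF-2) for each block-mate goes from 3/4 = 75% to 3/3 = 100%.
- One FGF-2 subject is revealed: P(placebo) for each block-mate goes only from 1/4 = 25% to 1/3 = 33%.
- The placebo subject is identified with certainty only if all three FGF-2 block-mates fail. At 81% closure that is 0.19³ = 0.7% of blocks.

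**3. How often the placebo subject is revealed.** This is 1 − placebo closure. With the 10% control closure of the clinical study in Section 3.2 it is 90% of blocks. With the 41% of the chinchilla study in Section 3.1 it is 59%.

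**4. Who is still under assessment.** Take nominal visit days and a code break at the placebo subject's Day 64. A block-mate who enters L days later is seen after the break at:
- Visit 2 if L > 64 − 22 = 42 days;
- Visit 3 if L > 64 − 43 = 21 days;
- Visit 4 for any L > 0.

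The final visit falls two months (taken as 61 days) after the last follow-up visit. A block-mate closed at Visit 2 has it on Day 22 + 61 = 83, so it comes after the break even for someone who entered up to 83 − 64 = 19 days earlier.

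**5. Share of subjects reached before the last Part A assessment.** The documents give no accrual rate, so this was simulated under stated assumptions:
- one list of 60, with list position known to the observer;
- random (Poisson) accrual at 1 to 4 subjects per month;
- the closing visit equally likely to be Visit 2, 3 or 4;
- non-closers revealed 63 days after first application;
- closure of 98% v 10%, 92% v 10% and 81% v 41%. These are rates cited in Section 3; the 92% series has no control group, so its 10% is borrowed.

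An arm counts as deducible if the block's placebo subject, or all three FGF-2 block-mates, had been revealed earlier. The result is about 12–25% of all subjects and 16–33% of FGF-2 subjects. In numbers, 0.12 × 60 to 0.25 × 60 is about 7 to 15 subjects, nearly all on FGF-2 (0.16 × 45 to 0.33 × 45 gives the same).

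**6. Sensitivity.** A second model gives each application the same chance of closing the ear, so more ears close early. It spreads entry evenly over 12 to 48 months (60/12 = 5 down to 60/48 = 1.25 per month). List position is again taken as known. Share of FGF-2 subjects assessed after their arm is deducible:

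| Assessment | 92–98% v 10% | 81% v 41% |
|---|---|---|
| Visit 2 | 0.3–17% | 0.2–11% |
| Visit at which closure or failure is settled | 5–25% | 10–19% |
| Final visit | 64–87% | 46–57% |

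Slower accrual raises the Part A figures and lowers the final-visit figures. The final-visit row matters for the primary endpoint only if that visit is the test of cure. Section 13.2 calls the test of cure Visit 5, while Section 14.5 reserves Visit 5 for crossed-over subjects, so those sections must be reconciled.

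**The case against.** The strongest reply is that the decisive premise, known list position, is not in the documents. Two sites (Section 26) draw on one central list. A local investigator sees local entries only and cannot tell where a block starts. Nothing says that the randomization number on the case report form is the spreadsheet line. In a re-run with two sites sharing the list (assumed 70:30 or 50:50), an investigator who treated local order as list order called block-mates correctly 73–86% of the time, against 75% from the 3:1 ratio alone. At four subjects per month with 92–98% v 10% closure it was 73–76%, so almost nothing is learned. This stands, and it is why the percentages are an upper bound.

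Second, knowing the arm distorts the result only if an ear is then misjudged. With list order known and FGF-2 closure of 81–98%, FGF-2 subjects both deducible and unclosed are about 1–6% (0.4 to 2.6 of 45). A false call would also have to survive the durability requirement and the final examination, photograph and tympanometry. This also stands.

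Third, a reader might infer that the treating investigator alone judges closure by eye. The documents do not say so. They name photography and do not say who adjudicates. The lack of a named masked reader is a related but separate gap, and masked reading would help whatever the block size.

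None of this removes the conflict between the commitment in Section 6 and a published block rule combined with scheduled code breaks. The only protection described is that the pharmacy holds the list.

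**Conclusion.** The point holds in conditional form. For anyone who can place subjects on the list, a placebo failure revealed at Visit 4 makes its three block-mates certain to be on FGF-2, at odds with the blinding promised through Part A. About 12–25% of all subjects and 16–33% of FGF-2 subjects could be affected before their last Part A assessment. That is a ceiling: it rests on known list position, assumed accrual of 1 to 4 per month and an even spread of closing visits. With earlier closure the FGF-2 share falls to 5–25%. It falls further if neither site sees the other's entries.

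A reader might go on to infer that investigators will in fact know these arms, or that the closure comparison is biased by a known amount. The documents support neither. They do not link the randomization number to the list line, do not give accrual, and do not say who adjudicates closure.

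This is a minor-to-moderate design weakness. It is worth correcting mainly because the correction costs so little.

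**What to change.** - Generate the list with randomly varying block sizes that keep 3:1, for example 4 and 8. In a block of 8, one revealed placebo leaves each block-mate at 6/7 = 86% rather than 100%, and varying sizes hide where blocks begin.
- Keep the sizes and the list in the pharmacy only. Replace the block description in Section 10.2 with wording such as *permuted blocks of varying size, 3:1*.
- In the same edit, reconcile 15 sets of four (60) with 75. The Synopsis gives both 75 and 45 + 15 = 60, and Section 17.1 gives 60. A list made of complete blocks must be a multiple of four (60, or 76 to cover 75).
- State that the randomization number shown outside the pharmacy does not reveal list order.

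The cost is one regenerated list and one edited paragraph. Arm balance at the interim look (n = 30, Section 17.5) loosens slightly. Blocks of four give 7 or 8 placebo subjects (seven full blocks plus two subjects). With blocks of 4 and 8 the range is 6 to 9: 24 subjects in full blocks give 6 placebo plus 0–2 from an open block of 8, and 28 give 7 plus 0–2.

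The change reduces inference from Visit 4 code breaks but does not eliminate it, because each break still reveals one line of the list.
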